### **4. DETERMINATION OF SAMPLE SIZE**

[REDACTED]

## 5. TYPE OF PLANNED ANALYSIS

This analysis plan outlines planned analysis procedures for the Final Analysis, as described below. Data outliers and other raw data issues are planned to be identified and logged on a rolling basis throughout the study, with appropriate resolution decided upon and documented prior to the planned analyses outlined below. The Final Analysis will take place after the study is completed and the database has been locked. All tables, figures, and listings described in this SAP are planned to be included in the final analysis.

## 6. GENERAL CONSIDERATIONS FOR DATA ANALYSES

[figure not shown]
## 6.1. Data Presentation and Summarization

The statistical analyses will be reported using summary tables, listings, and figures (TLFs). The International Conference on Harmonisation (ICH) numbering convention will be used for all TLFs. Continuous variables will be summarized with means, standard deviations, medians, minimums, and maximums. Other summaries (e.g., quartiles, 5%, 95% intervals, CV or %CV) may be used as appropriate. Categorical variables will be summarized by counts and by percentage of patients in corresponding categories. Summaries will generally be presented by treatment cohort and for all participants overall. P-values will be presented for hypothesis testing, with a value of 0.05 being the threshold of significance under which the null hypothesis can be rejected.

All analyses and tabulations will be performed using SAS® Version 9.4 or higher. Tables, listings, and figures will be provided in PDF format.

## 6.2. Missing or incomplete dates

The most conservative approach will be systematically considered.

### 6.3. Analysis Sets

Analysis sets define the participants to be included in an analysis. Analysis sets and their definitions are provided in this section. The analysis set will be identified and included as a subtitle of each table and listing.

Inclusion in the analysis set will be determined prior to database lock. A summary of the number and percent of participants in each analysis set will be provided. A by-participant listing of each analysis set will also be provided.

#### 6.3.1. Enrolled Population

This population consists of all subjects who are enrolled in the study (signed informed consent).

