### 5.2 Inclusion Criteria

In order to be enrolled in the study, the subject must:

1. Be willing and able to sign the informed consent and comply with study procedures.
2. Be at least 18 years of age.
3. Be male or female and meet the following conditions:
  - a. Female participants must be of non-childbearing potential, or,
  - b. If of childbearing potential be non-pregnant or lactating and agree to use highly effective contraception from screening through Day 30.
  - c. Male participants, if not surgically sterilized, and if engaging in sexual intercourse with a female partner of childbearing potential, must be willing to use highly effective contraception from screening through 30 days post-dose and agree not to donate semen during this waiting period.
  - d. Highly effective contraception involves the use of a condom for the male, plus one of the following for the female:
    - Oral, injectable, implantable, intravaginal, or transdermal hormonal contraceptives, or
    - Intrauterine device or intrauterine hormone-releasing system.

NOTE: Participants who abstain from heterosexual intercourse as their usual and preferred lifestyle, will not be required to use contraception as described above. They are required to maintain abstinence from screening through Day 30, AND

Participants in a same sex relationship, must use a barrier form of contraception (e.g., condom, diaphragm) to protect against the transfer of the study drug in any bodily fluids.

4. Have a lung nodule or mass that might be considered primary lung cancer or lung metastases, whether or not it is biopsy-proven.
5. Be scheduled to undergo standard of care surgical resection for a lung nodule or mass with diagnostic and/or curative intent for lung cancer and meet all pre-operative surgical and anesthesia acceptance criteria.
6. [REDACTED]
7. Have an ECOG score of 0-2.
8. Meet all standard surgical and general anesthesia requirements.
9. Have not participated in a clinical trial within the last 30 days.

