#### 6.1.1 Informed Consent

Prior to performing any study-related activities under this protocol, including screening tests and assessments, written informed consent with the IRB-approved ICF must be obtained from the subject in accordance with local practice and regulations.

All subjects must be provided a written Informed Consent Form (ICF) describing the study with sufficient information for them to make an informed decision regarding their participation. Subjects will be given the opportunity to ask questions about the study prior to participation.

A copy of the ICF, signed and dated by the subject, must be given to the subject and documented in the subject's source documentation. The original signed consent form will be retained with the study records.

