#### 6.1.2 Screening (Days -60 to -1)

Once informed consent is obtained the following assessments will be done to establish a subject's eligibility for the study. Note: in cases where subjects have given consent for general pre-screening at the site, some of these assessments may be done by chart review.

When possible, the assessments should be done in the order listed here to avoid the demands of sample collection and ECG prior to the subject passing basic entry criteria requirements.

1. Review of eligibility requirements – inclusion and exclusion criteria.
2. Collection of demographic information and medical and surgical history, including review of prior and ongoing medications (taken in previous 30 days).
3. Physical Exam.
4. Height and weight measurements.
5. Vital signs measurement (blood pressure, pulse rate, respiratory rate and oral/tympanic temperature).
6. Standard 12-lead ECG (subject should be resting in a supine position for at least 5 minutes prior).
7. Blood sample collection for clinical chemistry, hematology and coagulation.
8. Urine sample collection for urinalysis.
9. In women of child-bearing potential, blood sample for serum pregnancy test.

Upon establishment of eligibility, subjects will be assigned to a dose and scheduled for admission to the hospital.

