### **3. STUDY DESIGN**

This is a Phase 2, open-label study to evaluate the safety and efficacy of VGT-309, a tumor-targeted, activatable fluorescent imaging agent, to identify cancer in subjects undergoing lung cancer surgery. A total of 40 subjects will be enrolled to ensure at least 38 evaluable subjects with the option to expand enrollment by protocol amendment if deemed necessary to meet primary and/or secondary objectives. Following agreement with and signing of the informed consent, subjects will undergo screening measurements for the study.

Assessments include the following, unless they have been done within 4 weeks prior to the anticipated dosing:

1. Medical, surgical and medication history.
2. Complete physical exam, including vital signs and weight.
3. Standard pre-operative chemistry, hematology, coagulation, and urinalysis clinical laboratory studies.
4. 12-lead ECG.
5. Serum pregnancy test for females of child-bearing potential.

Following clearance of all enrollment criteria, each subject will receive an IV administration [REDACTED] VGT-309 at 12-36 hours prior to surgery (refer to section VGT-309 Dosing, below). Upon dosing, subjects will be observed for up to 2 hours and asked about possible treatment emergent adverse events. Subjects will undergo surgical resection as planned and within the time specified following VGT-309 dosing. Measurements of efficacy will be taken during surgery and during the pathological examination of all surgical specimens. (Refer to Efficacy Endpoints and Efficacy Assessments sections).

Following surgery, subjects will be monitored for safety during their hospitalization. After discharge from the hospital, and approximately 14 days post-surgery, the subjects will be contacted by telephone to assess their well-being. Between 19 to 39 days post-surgery, subjects will either return to the clinic or participate in a telehealth visit for final safety assessments. If there are no adverse events requiring further follow up, subjects will then be released from the study. If a subject chooses to withdraw from the study prior to the final visit, they will be asked to undergo a final safety assessment before their departure.

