## 7. STUDY POPULATION

In general, subjects who signed informed consent and were enrolled for the study will be used for data summaries and listings for subject disposition. Safety population will be used for safety summaries and listings, while Efficacy Population will be used for all efficacy analyses, unless otherwise specified.

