### 7.1. Subject Disposition

#### 7.1.1. Subject Enrollment and Disposition

A summary of subject disposition will be provided and will present the number of subjects enrolled, and the number and percent of subjects:

- Included in the Safety analysis set;
- Included in the Efficacy analysis set;
- Completing the study (includes the study treatment period and any post-treatment follow-up period); and
- Not completing the study, (with summary of reasons for not completing the study).

[REDACTED]

[REDACTED]

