### **7.3. Inclusion/Exclusion Criteria**

Subjects who did not meet inclusion/exclusion criteria will be listed for all screened subjects, along with the criterion number and description not met.

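### Does equating enrolment with signed consent in SAP 6.3.1 distort the disposition table enough to need a change?

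*SAP*

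**What the plan says.** SAP 6.3.1 defines the Enrolled Population: "This population consists of all subjects who are enrolled in the study (signed informed consent". The matching row of Table 01 in Protocol 10.2 does not mention consent.

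Elsewhere, enrolment means more than consent:

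- Protocol 5.2 introduces nine criteria with "In order to be enrolled in the study, the subject must". Being willing and able to sign the consent form is only part of the first. Protocol 5.3 adds exclusions.
- Consent precedes screening. Protocol 6.1.1 sets the timing ("Prior to performing any study-related activities under this protocol, including screening tests and assessments, written informed consent"), and 6.1.2 continues: "Once informed consent is obtained the following assessments will be done to establish" eligibility.
- SAP 3 places dosing later still: "Following clearance of all enrollment criteria, each subject will receive an IV administration".

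On reporting, SAP 7 names the subjects used for disposition: "subjects who signed informed consent and were enrolled for the study will be used for data summaries and listings for subject disposition". SAP 7.1.1 then gives the number enrolled, followed by the number and percent in the Safety set, in the Efficacy set, completing, and "Not completing the study, (with summary of reasons for not completing the study"). SAP 7.3 treats screening separately: "Subjects who did not meet inclusion/exclusion criteria will be listed for all screened subjects".

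**The concern.** Every screening test follows consent, so some subjects may sign and then prove ineligible. If enrolled means signed consent, the Enrolled Population is the same set as the screened subjects, although SAP 7.3 refers to screened subjects as a group of their own. The visible rows of SAP 7.1.1 offer a screen failure only one place, among those not completing. Read as two conditions, SAP 7 leaves the same subject out of the table.

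Two programmers could therefore report different completion rates from the same data. The reported number enrolled could also be hard to compare with the planned 40. If recruitment stopped at 40 consents, the allowance of two subjects between 40 enrolled and 38 evaluable could be used up by screen failures.

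**Working it through.** **Planned numbers.** Protocol 10.1 plans 40 subjects to obtain at least 38 evaluable. The derivation is redacted. The implied loss is 1 − 38/40 = 5%, and 38/(1 − 0.05) = 40. The two figures agree, but because the 5% is back-calculated this is not an independent reproduction.

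**Effect of the literal reading.** Let s be the number of consented subjects who fail screening. The documents give no value, so s = 0, 5, 10 and 15 are assumed. Assume also 40 dosed and 38 completing. Setting completers equal to the 38 evaluable is a simplification: Protocol 5.4 defines evaluable as dosed and imaged, whereas completion in SAP 7.1.1 includes follow-up.

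- Enrolled N = 40 + s
- Safety set = 40/(40 + s)
- Completing = 38/(40 + s)
- Not completing = (2 + s)/(40 + s)
- Screen failures among non-completers = s/(2 + s)

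| s | Enrolled N | Safety set | Completing | Not completing | Screen failures among non-completers |
|---|---|---|---|---|---|
| 0 | 40 | 40/40 = 100.0% | 38/40 = 95.0% | 2/40 = 5.0% | 0/2 = 0% |
| 5 | 45 | 40/45 = 88.9% | 38/45 = 84.4% | 7/45 = 15.6% | 5/7 = 71% |
| 10 | 50 | 40/50 = 80.0% | 38/50 = 76.0% | 12/50 = 24.0% | 10/12 = 83% |
| 15 | 55 | 40/55 = 72.7% | 38/55 = 69.1% | 17/55 = 30.9% | 15/17 = 88% |

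Under the eligibility-based reading, every row keeps Enrolled N = 40 and completing = 38/40 = 95.0%.

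**Can a reader see through it?** Yes. The table reports both the number enrolled and the number in the Safety set. Their difference is the number consented but not dosed: at s = 15, 55 − 40 = 15. Completion among dosed subjects, 38/40, can be worked out from the same table if the non-completion reasons are shown as planned.

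**Which section governs the table?** SAP 7.1.1 sits under SAP 7, whose opening paragraph names the disposition subjects and joins consent and enrolment with an "and"-type condition. The visible text of 7.1.1 does not refer back to 6.3.1. The parenthesis in 6.3.1 can also be read as a record required for enrolment, not as its only trigger.

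**Which analyses move?** SAP 6.3.2 and 6.3.3 both require VGT-309 to have been given. A screen failure is in neither set under either reading, so the change in those two counts is 0.

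**Does the planned 40 run short?** If 40 were counted at consent and nobody replaced, three screen failures would leave 40 − 3 = 37, below 38. But Protocol 5.4 allows replacement of subjects who do not meet the evaluable criteria, and an undosed subject does not meet them. The 40 exists to reach 38 evaluable, and the Efficacy count is reported.

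**What would tightening do?** The Safety Population is nested in Enrolled: SAP 6.3.2 requires both enrolment and some VGT-309. If enrolled required all eligibility criteria to be met, a subject dosed and later found ineligible would leave Enrolled and therefore Safety. With one such subject among 40 dosed, the Safety set would be 39. That subject could remain in the Efficacy Population, whose definition does not mention enrolment. SAP 7.2 plans for protocol deviations, so the case is foreseeable. The consent-based definition avoids it.

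**The case for a change.** The strongest case for a change is that the conflict lies in readable text, and redaction cannot remove it. SAP 6.3.1 is looser than Protocol 5.2 and 5.3. If the two-part wording of SAP 7 is dismissed as redundant, the SAP still departs from the Protocol. SAP 6.3 also promises the number and percent of participants in each analysis set without stating a denominator, so the ambiguity reaches that summary too. Replacement of non-evaluable subjects under Protocol 5.4 is optional, and screen failures are not named there. A safer wording, consented and confirmed eligible by the investigator, would cost only a few words.

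The inconsistency of definition stands. What does not stand is the size of its consequence. It requires a programmer to prefer 6.3.1 over the section that introduces the table, and it requires an assumed number of screen failures. Nor can the absence of a screen-failure line be relied on: text directly after the list in SAP 7.1.1 is redacted, Protocol 5.1 has a redacted paragraph, and the SAP's list of tables is unreadable. The visible plan already summarises reasons for non-completion, lists screened subjects with the criterion they failed, and gives a by-participant listing of each analysis set. Extra rows for screened or replaced subjects are a matter of presentation.

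**Conclusion.** No change follows. The parenthesis in SAP 6.3.1 is a loose gloss that analysts can resolve when they fix set membership, which SAP 6.3 requires before database lock.

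The effect on efficacy and safety results is zero, because both sets depend on dosing. The effect on disposition is a denominator: with 40 dosed, 38 completing and 5 to 15 assumed screen failures, completion would read 84.4% to 69.1% instead of 95.0%. That would happen only if 6.3.1 were used in place of SAP 7, and the neighbouring counts would reveal it.

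This rests on three assumptions: that the screen-failure numbers are illustrative, that completers equal the 38 evaluable, and that the redacted text does not contradict SAP 7. A literal eligibility condition in 6.3.1 would put the Safety Population at risk in order to tidy one table.

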#### 6.3.2. Safety Population

This population consists of all subjects who have enrolled in the study and received any amount of VGT-309.

#### 6.3.3. Efficacy Population

This population consists of all subjects who have received any amount of VGT-309 and have surgery with NIR imaging.

## 7. STUDY POPULATION

In general, subjects who signed informed consent and were enrolled for the study will be used for data summaries and listings for subject disposition. Safety population will be used for safety summaries and listings, while Efficacy Population will be used for all efficacy analyses, unless otherwise specified.

### 7.1. Subject Disposition

#### 7.1.1. Subject Enrollment and Disposition

A summary of subject disposition will be provided and will present the number of subjects enrolled, and the number and percent of subjects:

- Included in the Safety analysis set;
- Included in the Efficacy analysis set;
- Completing the study (includes the study treatment period and any post-treatment follow-up period); and
- Not completing the study, (with summary of reasons for not completing the study).

[REDACTED]

[REDACTED]

#### 7.1.2. Exposure to Study Drug

Extent of exposure to study drug will be summarized for the safety population. [REDACTED]

[REDACTED]

### 7.2. Protocol Deviations

All protocol violations and deviations will be summarized by classification category (major/minor) and listed.

### **7.3. Inclusion/Exclusion Criteria**

Subjects who did not meet inclusion/exclusion criteria will be listed for all screened subjects, along with the criterion number and description not met.

### **7.4. Demographics and Baseline Characteristics**

Subject demographic data (e.g., age, sex, race, and ethnicity) and baseline characteristics (e.g., body weight, height, BMI) will be summarized using descriptive statistics (sample size, mean, standard deviation, median, Q1, Q3, minimum and maximum) for continuous data and by the number and percent of subjects for categorical data. The summaries of demographic data and baseline characteristics will be provided for the safety analysis set.

### **7.5. Medical History**

Medical history will be summarized by Medical Dictionary for Regulatory Activities (MedDRA) system organ class (SOC) and preferred term (PT) (version 25.0). Participants will only be counted once at each level of summation. Summaries will be sorted by decreasing total incidence by SOC (overall) and then by PT (within each SOC); for SOCs or PTs (within SOC) with the same frequency, sorting will be performed alphabetically. By-participant listings of this information will also be provided along with onset and resolution dates and grades (collected in the CRF if the condition is ongoing).

### **7.6. Prior and Concomitant Medications**

Concomitant medications are defined as medications that started on or after the treatment start date or were ongoing at the date of treatment start. Prior medications are defined as medications that started and stopped prior to the date of treatment start.

Medications will be coded using the World Health Organization (WHO) Drug Dictionary B3 Global (updated March 2022) and Anatomical Therapeutic Chemical (ATC) Level 4 drug classes and preferred drug names (PN) will be attached to the clinical database. The number and percentage of subjects with at least one instance of medication use will be summarized by ATC class and PN (within ATC class) ordered by decreasing total incidence of ATC and PN (within ATC); ties in frequency will be broken alphabetically. Patients will only be counted once at each level of summation. By-participant listings will also be provided.

## **8. EFFICACY ANALYSES**

### **8.1. Definition of the Primary Efficacy Endpoint**

The proportion of subjects with at least one Clinically Significant Event (CSE) as defined by:

A. [REDACTED]  
[REDACTED]  
[REDACTED]  
[REDACTED]

C.

## 8.2. Statistical Hypothesis for the Primary Efficacy Endpoint

A diagram consisting of several horizontal black bars of varying lengths. In the center, there is a horizontal bar with a vertical line through its middle, creating two smaller segments. This central structure is flanked by two horizontal bars. The entire arrangement is centered and is surrounded by four groups of horizontal bars. The top and bottom groups each contain four horizontal bars, while the left and right groups each contain only one horizontal bar.

### 8.3. Analysis of the Primary Efficacy Endpoint

Efficacy analyses will be performed on the efficacy population.

#### 8.4. Secondary Efficacy Endpoints

#### 8.4.1. **Definition of Secondary Efficacy Endpoints**

Secondary efficacy endpoints include:

- Sensitivity: [REDACTED]
- Specificity: [REDACTED]

- Positive predictive value (PPV): [REDACTED]
- Negative predictive value (NPV): [REDACTED]

#### 8.4.2. Analysis Methods for Secondary Efficacy Endpoints

Term	Percentage
GMOs	85%
Organic	92%
Natural	95%
Artificial	78%
Organic	88%
Natural	90%
Artificial	75%
Organic	82%
Natural	84%
Artificial	72%
Organic	80%
Natural	82%
Artificial	70%
Organic	78%
Natural	80%
Artificial	68%
Organic	75%
Natural	77%
Artificial	65%
Organic	72%
Natural	74%
Artificial	62%
Organic	68%
Natural	70%
Artificial	58%

## 9. SAFETY ANALYSES

## 9.1. Adverse Events and Deaths

Adverse events will be summarized by the Medical Dictionary for Regulatory Activities (MedDRA) system organ class and preferred term. Events will be summarized on the basis of the date of onset for the event. Only treatment-emergent adverse events (TEAEs), defined as any adverse event that begins on or after the date of administration of VGT-309, will be collected and analyzed in this study. For purposes of this document, AEs refers to TEAEs. An overall summary of TEAEs will be provided. The following summaries (number and percentage of subjects) of TEAEs (by System Organ Class and Preferred Term) will be provided:

- TEAEs
- Treatment-related TEAEs
- TEAEs leading to study drug discontinuation
- Serious TEAEs
- Treatment-related Serious TEAEs

All AEs collected during the study will be presented in a listing. Additionally, a listing will be provided for any AEs leading to death.

### **9.1.1. Adverse Event Dictionary**

Clinical and laboratory adverse events will be coded using the Medical Dictionary for Regulatory Activities (MedDRA version 25.0). System Organ Class (SOC), High Level Group Term (HLGT), High Level Term (HLT), Preferred Term (PT), and Lower-Level Term (LLT) will be attached to the clinical database.

